The proposed study is a multi-site 36-week double-blind, placebo-controlled randomized trial followed by an 18-week open label extension with all patients receiving the GLP1RA treatment. Therefore, each subject will be treated for a total of 54 wk. Subjects will be required to travel to one of three research sites (Seattle, Nashville, St. Paul). A flowchart for scheduled study visits (SVs) is outlined below. Before study start, there will be an investigator kickoff and training meeting guided by [name] from Seattle Children's to coordinate and align all assessments and interventions. In addition, Seattle Children's radiology center will provide standardized protocols to the other two imaging centers for consistent imaging techniques and analyses. During the study and after ending the intervention, there will be bimonthly investigator phone or video conferences.

Time Frame/Duration

The timeline for research activities is four years. This is outlined as: Years 1-3: Enrollment and treatment at 3 study sites. Years 3 and 4: hormonal assays. Year 4: completion of final data analyses.

Each patient will be in the study for 56 weeks, including the screening visit.

Data Requirements

A database will be designed for this study using REDCap (Research Electronic Data Capture) hosted at the Institute of Translational Health Sciences of which Seattle Children's and University of Washington are partners. REDCap is a secure, web-based application designed to support data capture for research studies, providing validated data entry, audit trails, and mechanisms for securely importing and exporting data. It will reside on a secure server with exclusive access by research personnel at all study sites. Access is tailored for specific roles to maintain blinding. Subjects are identified with a study identification number.

Study Measures

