Meal test. At study visits 1, 3 and 4 (0, 18 and 36 wk), subjects will have an OGTT (900-1100 AM) in the fasting condition, followed at study visits 0 and 36 wk by a standardized mixed meal caloric preload (macaroni & cheese at 1100 AM) and a free buffet meal (at 1230 PM). The buffet meal is an objective measure of satiety as it assesses food intake and choice after a caloric preload. The standardized test meal preload will provide 12% of estimated daily caloric requirements,⁸¹ based on the Schofield-HW equation.⁸² The purpose of the test meal is to ensure that study participants are in an equally fed state (together with oral glucose, total preload will be 22-27% of estimated daily caloric intake). Ninety minutes later, an ad libitum buffet meal will be served consisting of a wide variety of food items and more than the child's estimated daily calorie requirements will be offered (5,000 kcal). Participants will have access to the buffet for 30 min, after which calorie intake and composition of consumed foods will be measured by weighing back uneaten food. Hunger and fullness will be assessed every 30 min from fasting state before starting the OGTT until the end of the buffet meal using visual analog scales (VAS)⁸³ to assess subjective appetite, reliable in children over age 7 y,⁸⁴ and used by us previously.⁸⁵

Metabolic outcomes. Blood glucose, insulin, lipid panel, hemoglobin A1c, and as a measure of low-grade inflammation C-reactive protein will be assessed by high-sensitive (hsCRP) testing at a central lab (Northwest Lipid Research Laboratories, Seattle). Glucose tolerance will be assessed by a 2-hour oral glucose tolerance test. After placement of an intravenous catheter (IV), a baseline blood sample will be collected for measurement of hemoglobin A1C, and insulin (processed by the central lab). A 2-h OGTT (1.75 g/kg Glucola [maximum 75 g]) will then be performed with sample collection at 0', 30', 60', 90' and 120' for measurement of glucose and insulin. Samples will be placed on ice, and will be centrifuged. Leptin, total adiponectin, α -MSH, and soluble leptin receptor (sOB-R) are potential indicators of leptin sensitivity,⁸⁶⁻⁸⁹ and will be assessed in fasting state (leptin, total adiponectin, and sOB-R, R&D Systems, Minneapolis, MN; α -MSH, Phoenix Pharmac., Belmont, CA, the assay cross

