Treatment dosage and duration are based on prescribing information and prior successful clinical trial weight loss results.^{31,110} The placebo-control group is an essential arm in this trial as study measures can change over time without drug intervention and it supports the evaluation of efficacy and safety. The drug and placebo kits will be supplied by AstraZeneca, or the current pharmacologic company responsible for ExQW. Exenatide vials or pens 2.0 mg powder for injection will be supplied. All subjects will have weekly phone calls when not coming for a study visit, to check adherence and any potential

adverse effects. Any evidence for adverse effects will be discussed with the PI of each site and safety clinical visits will be considered.

All study medication will be stored/locked in the investigational pharmacy under appropriate temperature conditions. Dispensing and accountability records will be maintained by appropriate staff members.

Analysis

Analysis plan and sample size calculations by Aim.

The research team includes personnel with statistical and data management expertise for overseeing data collection, storage methods, and the following analyses (see letter of support, [name]). Adherence data collected during the placebo run-in phase will be summarized descriptively. All subjects completing the run-in phase will go on to the randomized treatment phase. The primary analyses will use the intention-to-treat (ITT) approach; i.e., subjects will be analyzed according to their randomized assignment regardless of treatment received. In addition, data of all completers will be analyzed separately as a sensitivity analysis. While every attempt will be made to collect complete data and retain all subjects, all sample size and power calculations account for dropout. Statistical methods have been selected to allow for inclusion of partial data. All testing is two-sided and $\alpha=0.05$. Repeated measures analyses will be conducted using SAS (SAS Institute, Inc., Cary, NC, USA) or R (The R Foundation for

Statistical Computing).

Analysis populations: All eligible subjects randomized will be included in the ITT population. The ITT population will be the primary analysis population for all primary, secondary, and tertiary outcomes. The safety population will be the primary population for all safety analyses, and include all subjects who receive at least one dose of study drug or placebo.

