6. STUDY PROCEDURES

For the placebo-controlled portion of the trial, each subject will have a screening visit and 4 study visits (weeks 0 [baseline], 6, 18, 36 [end of randomized trial]). Week 36 will also mark the beginning of the open label extension phase which will continue until week 54.

Screening Visit: The study will be explained to patients and their families and written consent/assent will be obtained. Medical history and concomitant medications will be documented. Vital signs will be recorded, including blood pressure, heart rate, respiratory rate and temperature. Body weight (lightly clothed) and height will be measured with a calibrated electronic scale and calibrated stadiometer. Hip and waist circumference measurements will be completed. A physical exam including Tanner staging will be done. This visit will also include:

- Blood draw for safety labs (electrolytes, CBC, lipase, amylase, glucose, transaminases (ALT, AST), creatinine, hemoglobin A1c, and thyroid hormones [TSH and free T4, or in patients with panhypopituitarism, free T4 only])
 - Blood for carcinoembryonic antigen (CEA) and calcitonin samples
- Blood for DNA extraction will be obtained for genetic markers (only at select sites)
- Urine pregnancy testing (HCG) will be done
- Instructions for 24h dietary recall.

Sexually active female participants are required to use birth control, unless they have documented gonadotropin deficiency.

Parents and participants (if appropriate) will be taught how to mix and inject the study medication. Parents/participants should perform a return demonstration before mixing the actual study medication. All teaching will be documented. Prior to leaving the clinic, parents/participants will inject the first dose of study medication under supervision. Dosing will be documented on the dosing log. Participants will be dispensed 1 more vial of study medication (placebo) to be administered at home the following week. The dose will be identical to the dosing provided in the blinded portion of the trial.

[figure not shown]

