Study Visits (SVs): After the initial screening visit, there will be 5 study visits (see overview and measures in **Fig. 1**) to assess adherence, drug safety, outcomes, and to distribute the drug or placebo. Hypoglycemia medications will be adjusted as needed. During the duration of the treatment, subjects with persistent abdominal pain and nausea/vomiting will discontinue study medication and be evaluated for acute pancreatitis and cholecystitis. In children, most adverse effects are mild GI effects that are transient.¹¹⁷ Subjects not tolerating their current dose will be discontinued from study at PI's discretion. Study medication will resume if and only if no significant adverse event is found and subjects concur. Subjects need to fast and refrain from exercise for ten hours prior to study visits for fasting blood draws. Physical exams including Tanner staging, and inspection of injection sites will be done at all visits (except no Tanner staging at 6 weeks visit). If a subject withdraws from the study or is withdrawn by an investigator for any reason, subjects will be asked to complete SV4 study procedures, not including the DEXA scan.

Other measures assessed at SVs (see Fig. 1):

- Questionnaires (eating, activity): SVs 1, 3, 4,
- 24h dietary recall-done the week prior to : SVs 1, 3, 4, 5
- Anthropometry: SVs 1, 2, 3, 4, 5
- Vital signs: SVs 1, 2, 3, 4, 5
- Actimetry: SVs 1, 3, 4
- Blood for metabolic outcomes: SVs 1, 3, 4, 5
- OGTT: SVs 1, 3, 4
- Energy intake at free buffet meal: SVs 1, 4
- Whole body DEXA in order to evaluate body composition: SVs 1, 4
- DLW energy balance assessment: SVs 1, 4
- ECGs: SVs 1, 3, 4, and 5
- Safety labs (electrolytes, CBC, lipase, amylase, glucose, ALT, AST, creatinine, hemoglobin A1c, and thyroid hormones): SVs 2, 3, 4, 5
 - Additional serum will be obtained at all sites and stored at a central location (SCRI Seattle) for future use (3 ml in case anti-exenatide antibodies will need to be assessed)
- CEA: SVs 3, 4, 5
- Calcitonin: SV 5
- MRI (if needed): SV 1

Weekly Contact: Research participants will be contacted weekly by telephone/email to assess for potential adverse events, concomitant medications, and compliance with dosing. Participants will also be reminded about their urine collections, diet recalls, and return of the accelerometer during these phone calls.

Visit Schedule:

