Thyroid AEs: In rodents, GLP-1 receptors are expressed on thyroid C-cells and administration of GLP-1 agonists can cause an increase in calcitonin levels and C-cell hyperplasia.^{125,126} In human and primate tissue, however, few GLP-1 receptors are expressed on C-cells and GLP-1 agonists do not appear to increase calcitonin levels in vitro or in vivo.¹²⁷ Analysis of over 5,000 subjects treated with GLP-1 agonists and followed for up to 2 years did not reveal a pattern of calcitonin elevation or increased risk for C-cell hyperplasia or medullary thyroid carcinoma.¹²⁸ Although in humans there is no documentation of such a relationship, we will include calcitonin measures as safety measures.¹²⁸ Although Exenatide does not have an official FDA warning for medullary thyroid carcinoma, Bydureon has a boxed warning for the potential safety concern of thyroid C-cell tumors in animals (clinical correlate being MTC).

Kidney AEs: Exenatide is cleared by glomerular filtration. There have been post-marketing reports of altered renal function in patients taking exenatide. It is not clear whether the alteration in renal function is due to exenatide use, but the FDA recommends that exenatide not be used in patients with renal impairment.

Cardiovascular AEs: Exenatide may cause heart rate to increase by about 3 beats per minute. It is not known if this increase in heart rate causes any harm. In animal models, heart rate and blood pressure were increased by GLP-1 agonists. This effect was thought to be due to increased sympathetic tone.¹²⁹ In humans, however, numerous studies have demonstrated an improvement

in blood pressure with exenatide therapy.^{109,122,130} In one 30 week trial of exenatide versus placebo, the between-group difference was a 4.4 mmHg reduction in systolic blood pressure and 3.4 mmHg in diastolic blood pressure for the exenatide group.¹³¹ The same study did show a between-group difference in heart rate with a 3 beat per minute (95% CI, 0.8-5.2) increase in the exenatide group.¹³¹ The clinical importance of the increased heart rate is unknown. The long term effects of exenatide on cardiovascular events are unknown. Change of QT interval was small and clinically insignificant. Intervention over periods of more than 6 months has shown small favorable effects on cardiovascular risk factors and biomarkers, i.e. reductions from baseline in systolic blood pressure, total cholesterol and low-density lipoprotein cholesterol (LDL), as well as triglycerides.

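### The only post-baseline calcitonin in the readable schedule is at week 54, after the placebo arm has moved to ExQW, so this safety measure has no placebo-controlled comparison

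*Combined protocol and SAP*

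**What the plan says.** All references are to the combined protocol and SAP.

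- **Baseline sample.** The screening visit in section 6 includes "Blood for carcinoembryonic antigen (CEA) and calcitonin samples".
- **Later samples.** The list of measures by study visit (SV) in section 6 has "Calcitonin: SV 5" and no other calcitonin entry. The safety laboratory panel at SVs 2 to 5 does not name calcitonin. CEA, drawn with calcitonin at screening, is repeated at SVs 3, 4 and 5.
- **Withdrawals.** Under Study Visits in section 6, "subjects will be asked to complete SV4 study procedures, not including the DEXA scan".
- **Design.** Section 4, Study Design, describes a 36-week placebo-controlled phase "followed by an 18-week open label extension with all patients receiving the GLP1RA treatment".
- **Role of the measure.** Section 7, Thyroid AEs, says "we will include calcitonin measures as safety measures". The paragraph also reports reassuring human data and, in a separate later sentence, notes the boxed warning for Bydureon.
- **Role of placebo.** Section 4, Rationale for Medication, gives as one reason for the placebo arm that "it supports the evaluation of efficacy and safety".

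**The concern.** A placebo arm helps to interpret a safety laboratory measure only if the measure is taken while that arm is still on placebo. For calcitonin the readable schedule does not do this. Both arms are on ExQW at the only post-baseline draw, so they differ in length of exposure, not in whether they are exposed. Subjects who leave early exit through a visit whose procedures do not include the assay.

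At stake is the usefulness of a measure that the plan chose to include. The 36-week randomised phase, where exposed and unexposed subjects can be compared, would say nothing about calcitonin. CEA does have values from that phase, and the readable text gives no reason for sampling the two markers differently.

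**Working it through.** **1. Which week is SV5?**

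- Section 6 gives the placebo-controlled portion as "4 study visits (weeks 0 [baseline], 6, 18, 36 [end of randomized trial", followed by an extension to week 54.
- Section 4, Meal test, fixes the numbering: "At study visits 1, 3 and 4 (0, 18 and 36 wk". So SV4 is week 36.
- Section 6 counts five study visits after screening, so SV5 is the remaining one, week 54.

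One statement conflicts. Section 7, Blood draws, labels study visit 5 as 36 weeks and gives it 16–20 ml. Section 7, Potential Risks, gives that volume to week 54 and 32–36 ml to each of weeks 0, 18 and 36. The plan's stated total of 137–161 ml per subject tests the two readings:

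| Visit | Low (ml) | High (ml) |
|---|---|---|
| Screening | 16 | 20 |
| Week 0 | 32 | 36 |
| Week 6 | 9 | 13 |
| Week 18 | 32 | 36 |
| Week 36 | 32 | 36 |
| Week 54 | 16 | 20 |
| **Sum** | **137** | **161** |

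The total is reproduced exactly with a separate week 54 draw. Without it the sum is 137 − 16 = 121 to 161 − 20 = 141 ml. SV5 is therefore week 54, and the 36-week label is a mislabel to be reconciled.

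**2. Exposure at each possible draw**

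| Draw | Original ExQW arm | Original placebo arm |
|---|---|---|
| Week 36 (not scheduled) | 36 weeks | 0 weeks |
| Week 54 (scheduled) | 36 + 18 = 54 weeks | 54 − 36 = 18 weeks |

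**3. What each contrast estimates.** Let f(t) be the mean effect of t weeks of ExQW on calcitonin, with f(0) = 0, and let d be the drift since screening. Assume that drift is the same in both arms and adds to the drug effect.

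- Week 54: [d + f(54)] − [d + f(18)] = f(54) − f(18).
- Week 36: [d + f(36)] − [d + f(0)] = f(36).

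Drift cancels in both. If the effect has levelled off by 18 weeks, f(54) = f(18) and the week 54 contrast is zero even though the drug has an effect. The week 36 contrast would show it.

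**4. Subjects without a post-baseline value.** Section 5 plans 48 enrolled and 38 completing at 20% dropout. Check: 48 × 0.80 = 38.4, and 24 × 0.80 = 19.2 per arm, matching 38 and 19. Subjects not reaching SV5: 48 × 0.20 = 9.6, or 48 − 38 = 10. The sample size text allows dropout of up to 20%, so 10 is the planned ceiling.

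**5. What a week 36 draw would provide.** About 19 per arm if only completers have a value, and at most 24 per arm if every withdrawal attends.

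- 95% half-width for a difference in means, in SD units, 1.96 × √(2/n): 0.64 for n = 19 and 0.57 for n = 24.
- One-sided 95% upper bound on the rate of elevated values when none is seen in an arm, 1 − 0.05^(1/n): 14.6% for n = 19 and 11.7% for n = 24.

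**The case against.** The strongest reply is that the plan never promises a between-arm analysis of calcitonin. The measure is not in Table 1 or Table 2, has no hypothesis and no analysis, and its only defined use is as an exclusion criterion at screening. The remark that placebo supports the evaluation of safety is general. For an individual check with a single repeat, the end of the study is defensible, because every completer has then been exposed and the ExQW arm is at its longest exposure. This stands, and it keeps the point at the level of a cheap improvement.

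Other monitoring exists: thyroid hormones at SVs 2 to 5, CEA at SVs 3 to 5, physical examination at all visits, and stored serum. None replaces calcitonin. The stored serum is earmarked for antibody testing, and its suitability for calcitonin is not stated. Adverse-event monitoring is detailed in a separate Data and Safety Monitoring Plan, and the section 6 list refers to Fig. 1. Neither could be seen, so an additional calcitonin draw there cannot be excluded.

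Four stronger readings are tempting, and the documents do not support them.

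- A reader might infer that calcitonin was adopted because of the boxed warning. Section 7 puts the two in the same paragraph but does not link them; the measure is introduced as a precaution despite the absence of a documented relationship in humans.
- A reader might infer that the week 54 data cannot separate drug effect from drift. Drift common to both arms cancels; what is lost is sensitivity to an early effect that plateaus.
- A reader might take 10 missing subjects as a forecast. It is the planned ceiling.
- A reader might assume that a week 36 draw would capture every withdrawal. They are only asked to complete those procedures.

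**Conclusion.** The gap is real on the readable text. No subject has a scheduled post-baseline calcitonin from the placebo-controlled phase. The only later value supports a 54- versus 18-week exposure contrast among those who stay, and up to about 10 of 48 subjects may have no post-baseline value.

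The conclusion rests on three things: the section 6 list being complete, SV5 being week 54 (which the blood total confirms), and the plan's own dropout ceiling. The schedule finding would change only if Fig. 1 or the Data and Safety Monitoring Plan adds a draw.

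This is a modest safety-monitoring weakness that should be corrected because the remedy is cheap. It does not touch any primary, secondary or tertiary efficacy analysis, and the added data would be too few to settle a rare thyroid signal.

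**What to change.** 1. Add calcitonin to the SV4 (week 36) blood sample, and state in the schedule that it is drawn before the first open-label dose. CEA and the safety laboratory panel are already taken at that visit.
2. Summarise change from screening to SV4 by randomised arm in the safety population, descriptively, with a confidence interval and the number of subjects contributing in each arm. Report values from subjects who exit early with their actual time on treatment, since their SV4 procedures will not fall at week 36.
3. Keep the SV5 value as a descriptive measure by length of exposure.
4. Reconcile the label for study visit 5 in section 7, Blood draws, with the visit numbering elsewhere, and check that Fig. 1 and the Data and Safety Monitoring Plan agree.

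**Cost.** At most 48 extra assays, a small volume from an existing sample and one line in the schedule, with no new visit or venepuncture. The existing withdrawal rule then also yields a value for those who attend the requested SV4 procedures.

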7. RISKS/BENEFITS

Potential Risks

The subjects participating in this study will be exposed to physical, psychological, and financial risks. Participation in all aspects of the research will be voluntary. Subjects, their parents or their legal guardians will be advised that they can withdraw without penalty or refuse participation in any portion of the study at any time. Overall there are moderate risks to subjects. There is a risk of breach of patient confidentiality.

Potential risks to the participants enrolled in the study include:

1. Discomfort from hunger due to 10h fasting until 8:30 AM at four of the study visits (week 0, 18, 36, 54).
2. Pain, minor injury (bruising), nausea, infection or the development of a localized inflammation (thrombophlebitis) from placement of an intravenous catheter and obtaining serial blood samples. Rarely some people faint.
3. Loss of a small volume of blood (16-20 ml at the screening visit and week 54 visits; 9-13 ml at week 6 visit; and 32-36 ml per OGTT study visit at weeks 0, 18, and 36).
4. Patients will have a brain MRI if there was no recent MRI within 6 months prior to enrollment in the study. Potential risks from the MRI include anxiety, claustrophobic reactions or discomfort due to high noise, need to maintain a fixed posture, and/or interference between unidentified metal inside or outside the body and the scanner. The overall safety of MRI is well established. All MRI pulse sequences used are within FDA guidelines for time-varying magnetic fields. Additionally, echo-planar imaging (EPI) conveys the potential for damage to subjects' hearing as the EPI gradients produce noise in the 120 dB intensity range. Sound attenuating headphone

decrease the sound delivered by 40 dB, greatly reducing the intensity of the sound. Participants will be able to hear verbal commands given via the sound attenuating headphones that are at the volume level of conversational speech.

5. This research study involves exposure to very low dose radiation from two DEXA whole body scans. Each DEXA exposes the patient to the equivalent of less than one day of background radiation.
6. There is a slight risk of skin irritation during an ECG from the electrodes or gel that is used.
7. Participants may find it bothersome to answer the investigator's questions.
8. Discomfort, significant hyperglycemia, nausea, a reaction or sensitivity triggered by the oral dextrose solution. Discomfort, nausea, or a reaction from an unidentified food allergy or sensitivity to used study foods.
9. The DLW tracer is made up of the stable isotopes of hydrogen (^2H) and oxygen (^{18}O) and therefore does not give out harmful radiation. These stable isotopes are found naturally in our drinking water and in our bodies. These isotopes have been used extensively to measure body composition and energy expenditure in premature infants, newborns, toddlers, children, adolescents, and pregnant and lactating women with no adverse effects. The deuterium oxide has been used across the world to measure human breast milk intakes in infants from newborns to 12 months of age. The DLW tracer in fact is cleaner than any tap water and fountain water.
10. Risks associated with the study drug. In this proposed study, subjects will receive weekly subcutaneous injections of placebo or ExQW 2 mg starting at week 0. ExQW may hurt an unborn child. It can change the way warfarin is metabolized. Exenatide is FDA approved for treatment of people with diabetes. Because the treatment in this study is investigational, there may be risks that we do not know about at this time.

In a recent multicenter study including 461 adults with T2DM treated with ExQW for 26 weeks, 61% of patients had one or more adverse events (AEs).³¹ Related to 461 patients, most frequent were injection site reactions (10% injection-site nodule, 4% subcutaneous nodule, 3% injection-site pruritus, 3% nodule, 2% injection-site erythema), followed by 9% developed nausea, 7% nasopharyngitis, 6% diarrhea, 6% headache, 5% decreased appetite, 5% constipation, 4% vomiting, 3% dizziness, 3% upper respiratory-tract infection, 3% abdominal pain, 2% dyspepsia, 2% unexpected therapeutic response, and 2% bronchitis. These results were similar to another clinical trial of adults with T2DM treated with ExQW up to 2 years.³⁷ Here 80% of subjects reported at least one AE, most frequently nausea (17%), injection site nodule (12%) and nasopharyngitis (12%). Overall expected AEs associated with the GLP-1 agonist ExQW may include:

Gastrointestinal AEs: The primary limiting factor for using GLP-1 agonists in humans has been gastrointestinal adverse events, in particular nausea, vomiting, diarrhea, and constipation, which occurred primarily during the first 6–8 weeks of therapy and declined thereafter. In the DURATION study trials the rates of gastrointestinal adverse events associated with ExQW treatment were for nausea 9.3-26.4%, diarrhea 6.1-18%, vomiting 3.7-11%, and constipation 4.6-10.8%.^{34,109} For example, in a study of non-diabetic patients, 25% experienced nausea of mild to moderate severity.¹¹⁸ The severity and incidence of nausea does decrease over time.

Pancreatic AEs: Controversial data exist regarding the risk for developing pancreatitis during treatment with GLP-1 agonists.^{119,120} A recent integrated safety analysis from 19 completed randomized controlled trials, composite exposure-adjusted incidence rates for pancreatitis among exenatide twice daily users (n=3,261) and a pooled comparator group (n=2,333) were not statistically different.¹²¹ However, the current package insert recommends that ExQW be discontinued immediately if pancreatitis is suspected.

Risk for hypoglycemia: In a 24-week monotherapy study of exenatide in subjects with type 2 diabetes, there was an approximately 5% incidence of minor hypoglycemia.¹²² These episodes were all treated with oral glucose and subjects did not require any assistance from another person, glucagon or further medical attention. The addition of exenatide to metformin therapy does not increase the risk of hypoglycemia.¹²³ The overall reported rates for mild hypoglycemia were 0-5%; symptomatic hypoglycemia has not been seen in non-diabetic patients treated with exenatide.^{118,124}

Thyroid AEs: In rodents, GLP-1 receptors are expressed on thyroid C-cells and administration of GLP-1 agonists can cause an increase in calcitonin levels and C-cell hyperplasia.^{125,126} In human and primate tissue, however, few GLP-1 receptors are expressed on C-cells and GLP-1 agonists do not appear to increase calcitonin levels in vitro or in vivo.¹²⁷ Analysis of over 5,000 subjects treated with GLP-1 agonists and followed for up to 2 years did not reveal a pattern of calcitonin elevation or increased risk for C-cell hyperplasia or medullary thyroid carcinoma.¹²⁸ Although in humans there is no documentation of such a relationship, we will include calcitonin measures as safety measures.¹²⁸ Although Exenatide does not have an official FDA warning for medullary thyroid carcinoma, Bydureon has a boxed warning for the potential safety concern of thyroid C-cell tumors in animals (clinical correlate being MTC).

Kidney AEs: Exenatide is cleared by glomerular filtration. There have been post-marketing reports of altered renal function in patients taking exenatide. It is not clear whether the alteration in renal function is due to exenatide use, but the FDA recommends that exenatide not be used in patients with renal impairment.

Cardiovascular AEs: Exenatide may cause heart rate to increase by about 3 beats per minute. It is not known if this increase in heart rate causes any harm. In animal models, heart rate and blood pressure were increased by GLP-1 agonists. This effect was thought to be due to increased sympathetic tone.¹²⁹ In humans, however, numerous studies have demonstrated an improvement

in blood pressure with exenatide therapy.^{109,122,130} In one 30 week trial of exenatide versus placebo, the between-group difference was a 4.4 mmHg reduction in systolic blood pressure and 3.4 mmHg in diastolic blood pressure for the exenatide group.¹³¹ The same study did show a between-group difference in heart rate with a 3 beat per minute (95% CI, 0.8-5.2) increase in the exenatide group.¹³¹ The clinical importance of the increased heart rate is unknown. The long term effects of exenatide on cardiovascular events are unknown. Change of QT interval was small and clinically insignificant. Intervention over periods of more than 6 months has shown small favorable effects on cardiovascular risk factors and biomarkers, i.e. reductions from baseline in systolic blood pressure, total cholesterol and low-density lipoprotein cholesterol (LDL), as well as triglycerides.

Endocrine AEs: A recent study¹³² shows the GLP-1 receptor agonist Exendin-4 influences the gonadal axis, in both adult and prepubertal female rats. The effects of GLP-1 administration were on the hypothalamic Kiss-1 system, changed the amplitude of gonadotropin secretion, and influenced reproductive efficiency in female rats. This effect has not been reported in humans.

Allergic reactions and injection site reactions: Some people will have mild skin redness, itching or bruising at the site of medication injection.^{31,38} Rarely, the medication can cause an allergic reaction. Antibody formation does occur with exenatide, as is expected with an injected amino acid.¹³³ The prevalence of antibody formation was 27-28%.¹²² Antibody formation does not appear to decrease medication effectiveness.^{123,134,135} There has been one case report of anaphylaxis to exenatide administration. The subject was treated with epinephrine and corticosteroids and exenatide was discontinued. Injection site reactions are mild, include redness, bruising or pruritus, and occur in up to 10% of subjects.¹³⁶

11. Lastly, the financial risks associated with participating in this study are due to the potential of any health information being disclosed to health or life insurance companies or to current or potential employers. While this is a potentially serious risk, it is very unlikely, as we will keep all personally identifiable information physically separate from all health information. All information will be on password-protected computers, or in locked file cabinets in locked offices at the three study centers.

Methods to Minimize Risks

Risks will be minimized in a manner specific to each procedure referenced above. The risk to participants' privacy is minimal and every effort will be taken to maintain confidentiality. Risks to participants are minimized by screening and approaching only patients who qualify or have shown interest in being in the study via advertisements. The investigators of the three study sites are experienced in reviewing and obtaining consent and assent. All study procedures will be performed by staff experienced with such protocols and in pediatric research. The main risk is breach of patient confidentiality. However, this risk is minimized by keeping paper records in a locked office, and maintaining computerized records in the password protected REDCap database. Researchers are trained in HIPAA privacy regulations and other applicable privacy policies. No information will be released, nor will participation in the research be acknowledged, to any party except where compulsory according

to law or University policy. There may be unknown or unanticipated adverse effects from participation in this study for which the Principal Investigators and study team will remain observant.

Any unanticipated adverse events will be reported by the site PI's according to applicable IRB policy. The Principal Investigators are fully engaged in the actual performance of the study and this ensures that adverse events would be readily known and reported by the Principal Investigators. As per the Office for Human Research Protections (OHRP) guidelines, appropriate assent and parental consent will be obtained in this study.

Blood draws: The minimum amount of blood needed for assays will be drawn. Blood will be collected through phlebotomy (screening and visits at weeks 6 and 54) or a small intravenous line (visits at weeks 0, 18, and 36) after anesthetizing the skin with anesthetic cream. Blood draws during study visits at weeks 0, 18, and 36 (OGTT tests), require a total amount of 32-36 ml blood: 16-20 ml blood at baseline, and additionally, 4 blood draws of each 4 ml at 30, 60, 90, and 120 min after the oral glucose load. Lab parameters at the screening visit and study visit 5 (36 weeks) require each 16-20 ml blood, and 9-13 ml at study visit 2 (6 weeks). Total estimated amount of blood per subject equals to 137-161 ml or less during the whole 12-month study.

Hyperglycemia: The oral glucose load (1.75 g/kg, max. 75 g) can lead to significant hyperglycemia. All patients will be screened for diabetes before the study will be started. Any patient that meets the criteria for diabetes mellitus will be excluded from the OGTT and referred to the diabetes outpatient clinic for treatment. Any subject with insulin-treated diabetes mellitus or poorly controlled type 2 diabetes will be excluded from the study (see exclusion criteria). If patients develop diabetes during the study, management will be coordinated with their primary endocrinologist.

Nausea and abdominal discomfort: Due to the transient nature of the abdominal discomfort and nausea related to the study drug, and in order to prevent self-imposed drug holidays, all patients who experience nausea or abdominal discomfort are asked to contact the study team. The PI at each site will personally discuss appropriate therapy for this self-limited side effect.

Meals: At weeks 0, 18 and 36, subjects will have an OGTT (9:00-11:00 AM) in the fasting condition, which will be followed at weeks 0 and 36 by a standardized mixed meal caloric preload (macaroni & cheese at 11:00 AM) and a free buffet meal (at 12:30 PM). The test meal (macaroni & cheese) will be followed by an ad libitum buffet meal will be served consisting of a wide variety of food items and more than 100% of the subject's estimated daily calorie requirements. Children will have access to the buffet for 30 min., after which calorie intake and composition of consumed foods will be measured by weighing back uneaten food. Subjects will be screened for food allergies and sensitivities. In addition, all meals will be prepared fresh by the Clinical Research Center Nutrition Research Kitchen, and stored under adequate conditions. Duration of fasting is limited to 9:00 AM, and subjects can have water.

Neuroimaging: All subjects have had previous brain MRI scans before participation in this study. However, all subjects and their parents will be fully informed prior to beginning the study about the MRI procedure to reduce anxiety. Subjects in the MRI magnet will be able to talk to the experimenters at all times during the assessments, and are monitored by video. Should claustrophobia occur, subjects will be instructed that they can communicate to the MR technologist if they want to stop the scan. Subjects will have the option to discontinue the experiment at any time, and they will not be discouraged from doing so. There are planned procedures to minimize potential risks of metal

interference with the scanner by training the subjects and screening them properly before they go into the MRI scanning room. Subject safety requires that all ferrous materials be excluded from the immediate environment of the magnet. Hence, all subjects will be carefully checked prior to entering the magnet to make sure that no metallic objects remain on their person. Every subject will be screened for the presence of metallic objects. Any potential subject with contraindication to neuroimaging by MRI will be excluded from the study at the time of eligibility determination. Participants will be able to hear verbal commands given via the sound-attenuating headphones that are at the volume level of conversational speech. During MR scanning, the subjects will be monitored by video and audio. If any problems arise, the study will be terminated immediately. Additionally, the subjects will be given a call button that can be used at any time to stop the study.

The Principal Investigators will be accessible to answer questions and relieve anxiety whenever possible. Subjects, or their parents/legal guardians, may withdraw at any time or refuse to participate in all or part of any procedure without penalty. Subjects, or their parents/legal guardians, will have the option to discontinue the experiment at any time, and they will not be discouraged from doing so.

Potential Benefits

Individuals: The subjects will have a DEXA scan which provides information on their bone density and body composition. They will receive information about their metabolism, such as how many calories they burn per day. All subjects will receive the study medication during the second phase of the study. Subjects receiving Exenatide may experience weight loss.

